1. STUDY SYNOPSIS

NAME OF COMPANY

Sarepta Therapeutics Inc. [name] [contact]

NAME OF FINISHED PRODUCT

Eteplirsen Injection

NAME OF ACTIVE INGREDIENT

Eteplirsen

TITLE: An Open-Label, Multicenter, Study with a Concurrent Untreated Control Arm to Evaluate the Efficacy and Safety of Eteplirsen in Duchenne Muscular Dystrophy

PROTOCOL NUMBER: 4658-301

PHASE OF STUDY: Phase 3

INVESTIGATOR STUDY SITES: This study will be conducted at approximately 35 study sites in North America.

OBJECTIVES:

The primary objective of this study is to evaluate the effect of eteplirsen on ambulation, endurance, and muscle function as measured by change from Baseline to 96 weeks in the 6-minute walk test (6MWT) as compared to an untreated control arm of Duchenne muscular dystrophy (DMD) patients amenable to exon skipping.

The secondary objectives are to evaluate:

- the effect of eteplirsen on dystrophin expression as measured by the change from pretreatment in percentage of dystrophin-positive fibers (immunofluorescence histochemistry [IHC]) and dystrophin quantification by Western blot in biopsied muscle tissue
- the effect of eteplirsen on respiratory muscle strength as measured by the difference in change from Baseline in forced vital capacity % predicted and in maximal inspiratory and expiratory pressure % predicted between the eteplirsen treated and the untreated control arm of DMD patients amenable to exon skipping
- the safety and tolerability of eteplirsen

The additional objective is to evaluate the clinical and pharmacodynamic effects of eteplirsen treatment for up to 96 weeks.

METHODOLOGY:

This is an open-label, multicenter study to evaluate the efficacy and safety of eteplirsen in patients with genotypically confirmed DMD with exon deletions amenable to exon 51 skipping (treated group), with an untreated control arm of DMD patients amenable to exon skipping (untreated control group).

Patients will be evaluated for inclusion during a Screening/Baseline period of up to 10 weeks (not including time needed for genotyping if the patient has not been previously genotyped). Eligible patients for the treated group will receive once weekly intravenous (IV) infusions of 30 mg/kg eteplirsen for 96 weeks, followed by a safety extension (not to exceed 48 weeks), until the product is commercially available or until patients can transition into a separate eteplirsen study. Eligible patients for the untreated control group will not receive treatment with eteplirsen, but will complete study assessments through 96 weeks.

For all patients, efficacy, including the 6MWT, will be assessed at regularly scheduled study visits by a blinded rater. To minimize assessment bias, every effort will be made to keep the clinical evaluators unaware of the treatment arm of the patients, and all biological efficacy endpoint evaluations will be

Sarepta Therapeutics Inc. [name] [contact]

NAME OF FINISHED PRODUCT

Eteplirsen Injection

NAME OF ACTIVE INGREDIENT

Eteplirsen

performed by blinded assessors. Upon qualification for the study during the Baseline visit, patients in the treated group will undergo a muscle biopsy, and will be randomized to a second muscle biopsy at Week 24, 48, 72, or 96 in a 1:2:1:1 ratio. Patients in the untreated control group will not undergo muscle biopsy at any time point.

Safety will be monitored for all patients throughout the study through the collection of adverse events (AEs), concomitant medications, physiotherapeutic interventions, laboratory tests, electrocardiograms (ECGs), echocardiograms (ECHOs), vital signs, and physical examinations.

Blood samples for assessing plasma drug concentrations will be obtained at a subset of sites from at least 24 patients in the treated group. On Week 1, a single predose blood sample will be taken within 2 hours prior to the start of administration of the first dose. Both predose and postdose samples will be taken on Weeks 40, 48, 60, 84, and 96 as follows: within 2 hours prior to the start of the infusion, and approximately 5 to 10 minutes, 1 to 2 hours, and 2 to 4 hours after completion of the infusion; at Weeks 48 and 96, samples will also be taken at the end of the infusion prior to flushing the infusion line. Postdose samples alone will be taken on Weeks 8, 16, 24, 32, and 72, approximately 5 to 10 minutes after the completion of the infusion (the approximate time of post-dosing maximum plasma concentration for eteplirsen). Additional post dose samples will be taken on Weeks 8 and 24, approximately 1 to 2 hours after the completion of the infusion and on Week 72 at 2 to 4 hours after the completion of the infusion.

DURATION OF STUDY:

Screening/Baseline Period: up to 10 weeks (not including time needed for genotyping if the patient has not previously been genotyped)

Treatment Period: at least 96 weeks Safety Extension: not to exceed 48 weeks

Safety Follow-up Period: 4 weeks following the last infusion

Total patient participation: approximately 158 weeks

NUMBER OF PATIENTS: Approximately 110 patients will be included in this study, including approximately 90 patients with a Baseline 6MWT distance between 300 and 450 meters (~70 patients in the treated group and ~20 patients in the untreated control group) and approximately 20 patients with a Baseline 6MWT distance >450 meters (~10 patients in the treated group and ~10 patients in the untreated control group).

INCLUSION/EXCLUSION CRITERIA:

Inclusion Criteria:

A patient must meet all of the following criteria to be eligible for this study.

- 1. Be a male with DMD and meet one of the following criteria:
 - Have an out-of-frame deletion that may be treated by exon 51 skipping (e.g., deletions of exons 45-50, 47-50, 48-50, 49-50, 50, 52, 52-63). These patients will be enrolled into the treated group.
 - Have an out-of-frame deletion that is not amenable to treatment by exon 51 skipping but is amenable to treatment by skipping other exons (i.e., whole exon deletions in which the

Sarepta Therapeutics Inc. [name] [contact]

NAME OF FINISHED PRODUCT

Eteplirsen Injection

NAME OF ACTIVE INGREDIENT

Eteplirsen

reading frame may be restored by skipping 1 or 2 exons). These patients will be enrolled into the untreated control group.

- 2. Be 7 to 16 years of age, inclusive.
- 3. Have stable pulmonary function (forced vital capacity [FVC] % of predicted ≥50% and not require nocturnal ventilation) that, in the Investigator's opinion, is unlikely to decompensate over the duration of the study.
- 4. Have intact right and left bicep muscles (the preferred biopsy site) or 2 alternative upper arm muscle groups.
- 5. Have been on a stable dose of oral corticosteroids for at least 24 weeks prior to Week 1 and the dose is expected to remain constant (except for modifications to accommodate changes in weight) throughout the study. Note: patients may be allowed to take other (non-ribonucleic acid [RNA] antisense or non-gene therapy) medication including angiotensin-converting enzyme (ACE) inhibitors, angiotensin receptor blocking agents (ARBs), β blockers, potassium, and coenzyme Q, provided they have been on a stable dose for 24 weeks prior to Week 1 and the dose is expected to remain constant throughout the study.
- 6. Achieve a mean distance of 2 separate assessments on 2 consecutive days at the Screening and Baseline visits (prior to Week 1) ≥300 meters on the 6MWT with the 2 consecutive means being within 15% of each other, and with the Screening and Baseline 6MWT conducted 3 to 5 weeks apart. Personal assistance or use of any assistive devices for ambulation is not permitted during the 6MWT.
- 7. Male patients who are in the treated group and are post-pubertal and sexually active must agree to use, for the entire duration of the study and for 90 days post last dose, a male condom and the female sexual partner must also use a medically acceptable form of birth control (e.g., oral contraceptives).
- 8. Have a parent(s) or legal guardian(s) who is able to understand and comply with all the study requirements.
- 9. Be willing to provide informed assent (if applicable) and have a parent(s) or legal guardian(s) who is willing to provide written informed consent for the patient to participate in the study.

Exclusion Criteria

A patient who meets any of the following criteria will be excluded from this study.

- 1. Use of any pharmacologic treatment (other than corticosteroids) within 12 weeks of Week 1 that may have an effect on muscle strength or function (e.g., growth hormone, anabolic steroids).
- 2. Previous treatment with ezutromid (BMN 195/SMT C1100) at any time.
- 3. Previous treatment with drisapersen (PRO051) therapy within the last 3 months. To be eligible for the study, patients who were previously treated with drisapersen must be free of any of the following prior to Week 1: a) any active skin lesions related to drisapersen injection; b) renal signs/symptoms (including proteinuria or elevated creatinine/cystatin C); c) the presence of antiplatelet antibodies (to be tested at screening for patients who were previously treated with drisapersen); and d) abnormal platelet count.

Sarepta Therapeutics Inc. [name] [contact]

NAME OF FINISHED PRODUCT

Eteplirsen Injection

NAME OF ACTIVE INGREDIENT

Eteplirsen

- 4. Previous treatment with any other RNA antisense agent or any gene therapy within the last 6 months, or participation in any other DMD interventional clinical study within 12 weeks of Week 1, or use of the shock training system or "STS," or planned use during this study. Concurrent enrollment in any natural history, observational, or biomarker clinical trial is permitted, provided the patient's participation in the other trial does not affect any of the assessments performed in the 4658-301 clinical study. For patients in the untreated control group only, continuation in an interventional trial with standard-of-care medication may also be permitted if the patient's participation in the standard-of-care interventional trial does not affect any of the assessments performed in Study 4658-301, and the patient meets all the protocol-required entry criteria.
- 5. Major surgery within 3 months of Week 1, or planned surgery for any time during this study, except for protocol-specified surgeries, as applicable.
- 6. Presence of other clinically significant (CS) illness including significant cardiac, pulmonary, hepatic, renal, hematologic, immunologic, behavioral disease, or malignancy.
- 7. Use of any aminoglycoside antibiotic within 12 weeks of Week 1 or need for use of an aminoglycoside antibiotic or statin during the study.
- 8. Have a left ventricular ejection fraction (LVEF) of <50% based on the screening ECHO or QTcF ≥450 msec based on the screening ECG.
- 9. Loss of ≥30 degrees of plantar flexion from the normal range of movement at the ankle joint due to contracture (i.e., fixed plantar flexion of 10 degrees or more).
- 10. Change in contracture treatment such as serial casting, contracture control devices, night splints, stretching exercises (passive, active, self) within 3 months prior to enrollment, or expected need for such intervention during the study.
- 11. Prior or ongoing medical condition that could, in the Investigator's opinion, adversely affect the safety of the patient, make it unlikely that the course of treatment would be completed, or impair the assessment of study results. Additionally, patients who seem unwilling to comply with the study procedures, in the Investigator's opinion, are to be excluded.

DOSE/ROUTE/REGIMEN (TEST ARTICLE):

Eteplirsen 30 mg/kg will be administered as an IV infusion once a week for at least 96 weeks in the treatment period, and for up to 48 weeks in the safety extension.

REFERENCE TREATMENT:

The control group will be untreated.

CRITERIA FOR EVALUATION:

Efficacy:

The primary efficacy endpoint is the change from Baseline to Week 96 in 6MWT.

The secondary efficacy endpoints are the:

• Change from Baseline in dystrophin protein levels quantified by Western blot (treated patients only)

Sarepta Therapeutics Inc. [name]

[contact]

NAME OF FINISHED PRODUCT

Eteplirsen Injection

NAME OF ACTIVE INGREDIENT

Eteplirsen

- Change from Baseline in dystrophin intensity levels determined by immunofluorescence (treated patients only)
- Ability to rise independently from the floor (without external support) as indicated by a North Star Ambulatory Assessment (NSAA) subscore of "2" (without modification) or "1" (Gower's maneuver)
- Loss of ambulation
- Change from Baseline in FVC % predicted
- Change from Baseline in NSAA total score

SAFETY:

The safety and tolerability of eteplirsen will be assessed through evaluation of: the type, frequency, severity, timing, and relationship to investigational product of treatment-emergent adverse events (TEAEs), serious adverse events (SAEs), and AEs leading to discontinuation; concomitant medications and physiotherapeutic interventions; clinical laboratory testing including chemistry, hematology, coagulation, and urinalysis; vital signs; physical examinations; ECG; and ECHO (ejection fraction and fractional shortening).

Sarepta Therapeutics Inc. [name]

[contact]

NAME OF FINISHED PRODUCT

Eteplirsen Injection

NAME OF ACTIVE INGREDIENT

Eteplirsen

Pharmacokinetics:

Standard pharmacokinetic (PK) parameters will be estimated based on sparse sampling. The effects of demographic characteristics, concomitant medications, laboratory values, and other covariates on eteplirsen PK will be evaluated.

SAMPLE SIZE:

This study will enroll approximately 90 patients with Baseline 6MWT distance of 300 to 450 meters, including approximately 70 patients in the eteplirsen-treated group and approximately 20 patients in the untreated control group.

Additionally, approximately 20 patients (10 treated vs 10 untreated control) with Baseline 6MWT distance of >450 meters will be enrolled.

STATISTICAL METHODS:

Analysis of Efficacy Endpoints

The efficacy set for primary efficacy analyses will be patients with a baseline 6MWT distance of 300 to 450 meters, inclusive.

The analysis of change from Baseline to Week 96 (the primary time point of interest) in the 6MWT will be based on a mixed model repeated measures (MMRM) analysis, with treatment group, time, time by treatment group interaction, baseline 6MWT distance, and baseline 6MWT distance by time interaction as fixed effects; and patient as a random effect. Additional baseline variables may be added as covariates in the Statistical Analysis Plan (SAP). A heterogeneous autoregressive (1) variance-covariance matrix will be used. Estimates for changes from Baseline at each time point in each treatment group and for treatment differences will be provided with 95% confidence intervals and descriptive p-values using appropriate contrasts from the model. Due to the potential difference in progression based on DMD genotype in the control group, notably those with deletions amenable to skipping exon 44, additional sensitivity analyses may be performed.

As muscle biopsies will be confined to the treated group, the analysis of the secondary endpoints of change from Baseline in dystrophin protein levels by Western blot and dystrophin intensity levels determined by immunofluorescence will be based on a 1-sample permutation t-test. The analysis of the secondary endpoints of time from Baseline to loss of the ability to rise independently (from supine to standing) and time to loss of ambulation will be analyzed using the Kaplan-Meier method. The analyses of the secondary efficacy endpoints of change from Baseline in FVC % predicted and change from Baseline in NSAA total score will be similar to the primary endpoint.

Sarepta Therapeutics Inc. [name]

[contact]

NAME OF FINISHED PRODUCT

Eteplirsen Injection

NAME OF ACTIVE INGREDIENT

Eteplirsen

CCI

All efficacy data will be summarized descriptively by visit and treatment group.

Safety Analyses

TEAEs will be summarized by system organ class (SOC) and preferred term (PT) by treatment group. Non-treatment emergent events will be recorded in the data listings. For all AE tables, the number and percentage of patient-reported AEs will be grouped by the Medical Dictionary for Regulatory Activities (MedDRA) SOC and PT.

Descriptive statistics for ECG, ECHO, vital signs, and clinical laboratory parameters will be generated. Summary statistics for each parameter at a specific visit, as well as the change from Baseline to that visit, will also be displayed. All safety data will be presented in data listings.

Pharmacokinetic Analyses

Individual plasma levels of eteplirsen will be listed with the corresponding time related to eteplirsen administration, and summary statistics will be generated by per-protocol time of collection.

PK analysis of plasma concentration-time data of eteplirsen will be performed using nonlinear mixed-effects modeling. For population PK analyses, PK data from this study may be combined with those of other studies to support a relevant structural model. Available patient characteristics (demographics, laboratory variables, genotypes, concomitant medications, etc.) will be tested as potential covariates affecting PK parameters.

Interim Analysis

An interim analysis will be performed after approximately 35 patients with Baseline 6MWT between 300 and 450 meters, inclusive, have completed their Week 96 assessments. Given the small size of the untreated control group, external control patients, including those amenable to exon 51 skipping, may be identified and compared to the eteplirsen-treated group. The details of the interim analysis will be specified in a Statistical Analysis Plan before the database lock for the interim analysis.

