9.3.2. Administration of the Investigational Product

The dose of eteplirsen will be calculated based on the most recent patient weight obtained at the site prior to the current visit. Eteplirsen should be prepared for dosing by following the steps detailed in the study specific Pharmacy Manual.

Eteplirsen will be administered as an IV infusion over a period of approximately 35 to 60 minutes. It is recommended that a topical anesthetic cream (e.g., lidocaine 2.5%, prilocaine 2.5%, or LMX4 cream) be applied to the infusion site prior to each administration of eteplirsen.

An implanted venous access port may be inserted for eteplirsen administration at the discretion of the Investigator. If eteplirsen is administered into an existing IV line, the line should be flushed with normal saline before and after administration of eteplirsen. After eteplirsen administration and the saline flush, the port may be flushed with heparin to heplock the port prior to removal of the infusion line.

No other medications may be administered concomitantly during the eteplirsen infusion.

All treated patients will be observed for at least 1 hour following the end of each eteplirsen infusion.

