9.6.1. Maintaining the Blind for Clinical Evaluators

Clinical evaluators will be instructed on how to maintain blinding to treatment group as well as possible through training. Specifically, the clinical evaluators will:

- Not be involved in any aspect of care for the patients over the course of the study and will not have access to any clinical patient records including laboratory values, genetic analyses, or study-specific assessment and treatment schedules.
- Not have contact with the parents or caregivers of the patients.
- Avoid conversation with the patients about treatment, other assessments including muscle biopsies, and any other disease related topics.

 Strive to keep the conversation with patients to the necessary minimum to allow for optimal clinical assessments while keeping the topic relevant to the current evaluation.

Patients will be requested not to discuss their study treatment with the clinical evaluators.

In order to maintain the study blind, interaction between parents and clinical evaluators will be minimized. Parents of study participants will therefore be requested not to interact with clinical evaluators and will be asked to not publicly discuss their child's participation in this study. It will also be explained to parents that they will not receive any information on the clinical efficacy evaluation until the study is complete.

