10.2.2. Baseline Period (3-5 Weeks after Screening Functional Assessment Visit)

The muscle biopsy should be the last Baseline procedure performed.

At Hub Sites (Baseline Functional Assessment Visit; occurs within 4 weeks prior to Week 1):

The Baseline period may require a 2-night overnight stay near the Hub Site. Assessments will begin in the mornings on Day 1 and Day 2 in the order described in the Clinical Evaluator Manual.

Day 1:

- Assess eligibility
- Vital signs
- Height and ulnar length
- CCI
- 6MWT (Pulse will be recorded immediately prior to and after the 6MWT.)
- NSAA
- CCI

Day 2:

- CCI
- 6MWT (Pulse will be recorded immediately prior to and after the 6MWT.)
- NSAA
- CCI

Either Day 1 or Day 2:

• ECG

At Surgical Units (After eligibility has been confirmed) (for the treated group only):

The muscle biopsy should be the last Baseline procedure performed after the Local Site has confirmed eligibility. Assessments at the Surgical Unit should be performed in the order described in the Clinical Evaluator Manual.

- Informed Consent
- Safety laboratory assessments, including chemistry, hematology, coagulation, and urinalysis
- Immunogenicity
- A muscle biopsy will be performed on all patients in the treated group. The biopsy may be obtained as soon as eligibility is confirmed (i.e., Baseline assessment is complete and genotype is confirmed), prior to the first dose of eteplirsen. The first dose of eteplirsen must be within 4 weeks of the Baseline Functional Assessment visit. Surgery must be performed within the 4-week window between the Baseline Functional Assessment visit and Week 1. Patients in the treated group may not begin to receive eteplirsen until after the Baseline muscle biopsy has been performed.

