10.3.1. Primary Efficacy Assessment: 6-Minute Walk Test

The 6MWT will be performed by standardized procedures for all patients as outlined in Section 2. The patient will be asked to walk a set course of 25 meters for 6 minutes (timed), and the distance walked (in meters) will be recorded.

The same evaluator will complete the assessments on each patient throughout the study and at the same approximate time in the morning (which will be noted). The 6MWT will be performed on 2 consecutive days.

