10.3.2. Secondary Efficacy Assessment

10.3.2.1. Muscle Biopsy (Treated Group Only)

Upon qualification for the study during the Baseline visit, patients in the treated group will undergo muscle biopsy and will be randomized to a second muscle biopsy schedule at Week 24 (20%), Week 48 (40%), Week 72 (20%), or Week 96 (20%).

Biopsies at Weeks 24, 48, 72, and 96 must be taken:

- Within 2 weeks after the specified visit;
- After the clinical evaluation; and

• At least 48 hours after the most recent infusion.

The Baseline muscle biopsy will be obtained from one biceps brachii muscle and the subsequent muscle biopsy will be obtained from the contralateral muscle. A previously unbiopsied alternative upper arm muscle, may be used if the biceps brachii has been biopsied previously. If an alternative muscle group is used, the same contralateral muscle will be biopsied at the subsequent muscle biopsy.

Muscle biopsy samples will be collected at the Surgical Units and will be sent to a central laboratory for analysis. All analyses related to quantification of the dystrophin protein will be performed by personnel blinded to the time point of the patient's muscle biopsy (i.e., pre- and post-treatment). Details are provided in the Laboratory Manual.

Additional assessments completed on the muscle biopsy samples are presented in Section 10.3.3.6.

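### The rater-blinding safeguards limit records, contact and conversation, but none conceals biopsy scars or venous ports, so raters may become unblinded from Week 12

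*Protocol*

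**What the plan says.** The Protocol Synopsis (Methodology) assigns the efficacy tests, including the 6MWT, to a blinded rater and adds that "every effort will be made to keep the clinical evaluators unaware of the treatment arm of the patients".

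Section 9.6.1 lists the means: training; no part in the boy's care; no access to clinical records, genetic results or treatment schedules; no contact with parents; and little conversation, with biopsies named among the topics to avoid. On the boys' side, "Patients will be requested not to discuss their study treatment with the clinical evaluators". Section 10.2 adds that evaluators do not see earlier test results and that Hub and Surgical staff are kept separate from Local Site staff.

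The two arms undergo different procedures:
- **Treated.** Section 10.2.2 states that "A muscle biopsy will be performed on all patients in the treated group", as the last Baseline procedure. Section 10.3.2.1 adds: "The Baseline muscle biopsy will be obtained from one biceps brachii muscle and the subsequent muscle biopsy will be obtained from the contralateral muscle". Infusions are weekly, and in Section 9.3.2 "An implanted venous access port may be inserted for eteplirsen administration at the discretion of the Investigator".
- **Control.** "Patients in the untreated control group will not undergo muscle biopsy at any time point", and there are no infusions.

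Inclusion criterion 4 applies to both arms: "Have intact right and left bicep muscles (the preferred biopsy site) or 2 alternative upper arm muscle groups". On continuity of raters, Section 10.3.1 says "The same evaluator will complete the assessments on each patient throughout the study"; Section 10.2 makes this an aim rather than a fixed rule.

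**The concern.** Arm is assigned by genotype, and boys and investigators know it. The blinded rater is therefore the main stated protection against assessment bias in the functional endpoints. The protocol recognises that a biopsy would give the arm away, because it tells raters not to talk about biopsies. That closes the spoken route and leaves the visible one unaddressed.

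The endpoints at stake depend on the rater. The 6MWT is run by the evaluator and depends on the boy's effort. NSAA items, including rise from floor, are graded 2, 1 or 0 by the evaluator. SAP Sections 4.4.2, 6.3 and 7.8 drop the formal comparison with the concurrent controls, so the effect on that contrast is now descriptive only. SAP Section 4.4.2 still plans to use an external control dataset to evaluate the eteplirsen effect. Any rater bias in the treated boys' results would carry into that comparison.

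**Working it through.** No stated figure is in dispute. The check sets the safeguards beside the cues, and then counts who carries a study biopsy site at each functional visit.

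**1. Safeguards against cues**

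| Route to the arm | Covered in the protocol or SAP? |
|---|---|
| Records, genotype, schedules, earlier results | Yes (Protocol 9.6.1, 10.2) |
| Parents | Yes (9.6.1) |
| Conversation with the boy, including about biopsies | Yes (9.6.1) |
| Sight of a biopsy scar or port | No covering, clothing or dressing rule found |

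No check of whether raters have guessed the arm is planned either.

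**2. Timing.** The Baseline biopsy follows the Baseline 6MWT and NSAA and precedes the first dose. The first rater visit after it is Week 12. The post-Baseline functional visits are Weeks 12, 24, 36, 48, 72 and 96.

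**3. Allocation.** The 1:2:1:1 ratio has five parts: 1/5 = 20%, 2/5 = 40%, 1/5 = 20%, 1/5 = 20%. This reproduces the shares in Section 9.6.3 for Weeks 24, 48, 72 and 96.

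**4. Sites present when the rater sees the boy.** Section 10.3.2.1 places the second biopsy after the clinical evaluation of its visit. It is therefore present only from the next functional visit.

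| Visit | Treated boys with at least one site | Treated boys with sites on both arms | Of 70 planned (300 to 450 m) | Controls |
|---|---|---|---|---|
| Weeks 12, 24 | 100% | 0% | 0 | 0% |
| Weeks 36, 48 | 100% | 20% | 0.20 × 70 = 14 | 0% |
| Week 72 | 100% | 20 + 40 = 60% | 0.60 × 70 = 42 | 0% |
| Week 96 | 100% | 20 + 40 + 20 = 80% | 0.80 × 70 = 56 | 0% |

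These shares assume no dropout and no missed biopsy. They count study biopsy sites, not scars that a rater would actually see. The documents give neither that number nor the number of ports.

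**5. Continuity.** Where the same evaluator sees a boy at Baseline and afterwards, a mark that was absent at Baseline and present later can be noticed. A change of that kind says more than a single scar seen once.

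**The case against.** A reader might infer that the rater can identify the treated group from Week 12, or that the plan fails to deliver a blinded rater. The documents do not support either statement:
- Nothing shows that a scar or port would be visible to someone running a walk test with a boy in ordinary clothes.
- Section 10.3.2.1 allows for a biceps biopsied before the study, so one scar does not prove treatment. Ports are optional.
- Infusion marks are a weak cue. Hub visits for treated boys fall at least 48 hours after an infusion, and controls also have blood drawn.
- Ulnar length is listed before the 6MWT on Day 1 (Sections 10.2.7 and 10.2.10), but the operative order is set by the Clinical Evaluator Manual. The protocol does not say that the rater takes the measurement, and it concerns the forearm.
- The Manual and the training material are not among the documents and may already contain a covering rule.

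A reader might also want a figure in metres, but any such figure is an assumption. For example, an assumed shift of 5 to 15 m is 5/60 = 8% to 15/60 = 25% of the roughly 60 m decline over 48 weeks cited in Section 13.2. The endpoint is at Week 96. If decline were linear (a further assumption), 120 m would be the base, giving 4% to 12.5%. Neither range is evidence of bias.

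Finally, covering the arms does nothing about the boys' own knowledge of treatment, and the dystrophin assays are protected separately by blinding to time point.

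All of this limits the point to a risk of unblinding. It does not remove the gap: the written safeguards deal with information that is spoken or recorded, and the study itself creates visible marks in one arm only.

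**Conclusion.** The point holds as a risk. The safeguards in Sections 9.6.1 and 10.2 limit records, contact and conversation, and nothing in either document conceals biopsy scars or ports. Every treated boy who follows the schedule carries one study biopsy site from Week 12, and about 80% carry sites on both arms at the Week 96 assessment, against none of the controls. Raters may therefore become unblinded from Week 12, and this could bias the 6MWT, NSAA and rise results that go into the external-control comparison.

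The conclusion rests on three conditions: no dropout or missed biopsy for the shares, rater continuity being achieved where possible, and no covering rule in the Clinical Evaluator Manual. The documents show neither that unblinding occurs nor how large a bias would be. This is a cheap improvement to the plan, not a finding that the results are biased.

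**What to change.** Add to Protocol Section 9.6.1 and to the Clinical Evaluator Manual:
- At every Hub Site functional visit, boys in both arms put on identical covering of the upper arms and chest before they meet the evaluator.
- Ulnar length and any other bare-arm measure is taken after the 6MWT and NSAA. Both tests run on two consecutive days, so this means after the second day's tests.

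If the Manual already has such a rule, a cross-reference in Section 9.6.1 is enough.

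SAP Section 4.4.1 reports that the interim analysis, after approximately 35 boys had completed Week 96, has already been performed. A covering rule cannot repair visits already completed. For those, state the limitation in the supplemental SAP for the external control and in the study report.

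The cost is protocol and manual wording plus clothing, with no new visit or procedure. The downside is slightly warmer clothing during the walk, equal in both arms.
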